## 2 Study Objectives

### 2.1 Primary Objective

The primary objectives of the study are:

1. To determine the safety of and tolerability of AGS-v PLUS when administered as two doses alone, or with Montanide ISA-51 (single and two doses), or with Alhydrogel® (two doses) versus saline placebo (two doses).
2. To measure specific antibody and cellular responses in participants receiving two doses of AGS-v PLUS alone, or with Montanide ISA-51 (single and two doses), or with Alhydrogel® (two doses) versus saline placebo (two doses) from pre-vaccination to post-vaccination.

A previous study tested 2 doses of AGS-v, 21 days apart, as non-adjuvanted or in Montanide. For continuation, AGS-v plus will be tested with the same formulation as AGS-v but also with a different adjuvant, Alhydrogel®. In addition, a single dose of AGS-v plus in Montanide will be tested as animal data showed that only Montanide can trigger an antibody response to AGS-v after a single dose. In order to keep the blinding, participants in this group will receive saline on day 22.

### 2.2 Secondary Objectives

The secondary objectives of this study are:

1. To measure changes to the antibody and cellular immune responses after clean *Aedes aegypti* and *Aedes albopictus* mosquito feeding on participants receiving two doses of AGS-v PLUS alone, or with Montanide ISA-51 (single and two doses), or with Alhydrogel® (two doses) versus saline placebo (two doses).
2. To evaluate the effect of the AGS-v PLUS on *Aedes aegypti* and *Aedes albopictus* mosquito survival and fecundity after feeding on participants receiving two doses of AGS-v PLUS alone, or with Montanide ISA-51 (single and two doses), or with Alhydrogel® (two doses) versus saline placebo (two doses).

### 2.3 Exploratory Objectives

1. To evaluate reactions at the bite sites after mosquito feeding on participants receiving two doses of AGS-v PLUS alone, or with Montanide ISA-51 (one or two doses), or with Alhydrogel® (two doses) versus saline placebo (two doses).
2. To evaluate the effect of incubating Zika virus coated in vector saliva with peripheral blood mononuclear cells (PBMCs) and/or serum collected from individuals receiving two doses of AGS-v PLUS alone, or with Montanide ISA-51 (single and two doses), or with Alhydrogel® (two doses) versus receiving saline placebo (two doses).
3. To evaluate cellular immune responses to *Aedes aegypti*, *Aedes albopictus* and *Anopheles gambiae* mosquito salivary gland proteins in participants receiving two doses of AGS-v PLUS alone, or with Montanide ISA-51 (single and two doses), or with Alhydrogel® versus saline placebo (two doses).

placebo (two doses) will be assessed from pre-vaccination (day 1) to post-vaccination (day 43) and post-mosquito feeding (day 50).

### 3 Study Design

#### 3.1 Description of the Study Design

This is a randomized, double-blind, placebo-controlled, single-center, Phase 1 study of AGS-v PLUS administered at Days 0 and 21 before *Aedes aegypti* and *Aedes albopictus* mosquito challenge at Day 43. Participants will be randomized 1:1:1:1:1 to:

- Group 1: Saline placebo (N=10) on day 1 and day 22.
- Group 2: 1012 µg (50 nmol each peptide) unadjuvanted AGS-v PLUS vaccine (N=10) on day 1 and day 22.
- Group 3: 1012 µg (50 nmol each peptide) Montanide ISA-51 adjuvanted AGS-v PLUS vaccine (N=10) on day 1 and saline placebo on day 22.
- Group 4: 1012 µg (50 nmol each peptide) Montanide ISA-51 adjuvanted AGS-v PLUS vaccine (N=10) on day 1 and day 22.
- Group 5: 1012 µg (50 nmol each peptide) Alhydrogel® adjuvanted AGS-v PLUS vaccine (N=10) on day 1 and day 22.

A placebo control will be used to establish the frequency and magnitude of changes in endpoints that may occur in the absence of active vaccination. Randomization will be used to minimize bias in the assignment of participants to vaccination groups, to increase the likelihood that known and unknown participant attributes (e.g., demographic and baseline characteristics) are evenly balanced across vaccination groups, and to enhance the validity of statistical comparisons across vaccination groups. Blinding of participants and the study team will be used to reduce potential bias during data collection and evaluation of endpoints.

The study will be unblinded once all the data for the primary and secondary endpoints and safety data up to day 50 have been collected. Otherwise, the blind should be broken only if specific emergency treatment/course of action would be dictated by knowing the vaccination status of the participant. In such cases, the investigator may in an emergency determine the identity of the vaccine by opening the sealed code. It is recommended that the investigator contact the sponsor or its designee if possible to discuss the particular situation, before breaking the blind. In the event the blind is broken, the sponsor must be informed as soon as possible. Accidental unblinding (e.g. if the investigator sees the investigational product [IP] administration logs) must be reported within 1 working day to the Sponsor, who will advise on the corrective steps to be taken. The date and reason for the unblinding must be documented in the source document.

## 3.2 Study Endpoints

### Primary:

1. Incidence and severity of treatment emergent adverse events (AEs) and serious adverse events (SAEs).
2. Geometric mean titer and fold increase in serum AGS-v PLUS specific immunoglobulin G (IgG), immunoglobulin M (IgM) and immunoglobulin E (IgE) titers from day 1 to day 43.
3. Geometric mean concentration and fold increase in Th1 and Th2 cytokine responses (from day 1 to day 43) after *in vitro* exposure of PBMCs with AGS-v PLUS antigens.

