## PROTOCOL SUMMARY

Full Title:	Randomized, Double-Blind, Placebo-Controlled, Single-center, Phase 1 Study in Healthy Volunteers to Evaluate the Safety and Immunogenicity of AGS-v PLUS, a Universal Mosquito-Borne Disease and Mosquito Control Vaccine
Short Title:	AGS-v PLUS Mosquito Vax
IND Sponsor:	Office of Clinical Research Policy and Regulatory Operations Division of Clinical Research National Institute of Allergy and Infectious Diseases National Institutes of Health Laboratory of Infectious Diseases Clinical Studies Unit
Conducted by:	Center for Vaccine Development and Global Health
Principal Investigator:	[name], MPH
Sample Size for Data Analysis:	50 participants
Accrual Ceiling for Vaccinees / Placebo Recipients:	60 participants
Study Population:	Healthy volunteers 18 to 50 years of age
Accrual Period:	2 months
Study Design:	This is a randomized, double-blind, placebo-controlled, single-center, Phase 1 study of AGS-v PLUS administered as 2 vaccinations before a non-infected Aedes aegypti and Aedes albopictus mosquito feeding.
Study Duration:	The study will begin approximately in April 2019 and will require approximately 14 months to complete. The length of individual subject participation is about 12 months from enrollment. The study will be unblinded once the data from procedures up to day 50 related to the primary and secondary endpoints have been collected for all participants. After unblinding, two follow-up safety calls will be carried out on all participants on days 181 and 366.
Study Agents:	1012 µg of AGS-v PLUS (50 nmol of each of the five peptides in the formulation) non-adjuvanted, adjuvanted in Montanide ISA-51 or in Alhydrogel®.
Study groups:	Group 1. saline placebo (day 1 and day 22). Group 2. AGS-v PLUS non-adjuvanted (day 1 and day 22). Group 3. AGS-v PLUS + adjuvant Montanide ISA-51 (on day 1) and saline placebo on day 22. Group 4. AGS-v PLUS + adjuvant Montanide ISA-51 (on day 1 and day 22).

	Group 5. AGS-v PLUS + Alhydrogel® adjuvant (on day 1 and day 22).
Intervention Description:	Individuals will be vaccinated subcutaneously with vaccine or placebo 21 days apart.

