## **12 Assessment of Safety**

### **12.1 Documenting, Recording, and Reporting AEs**

At each contact with the participant, information regarding AEs will be elicited by appropriate questioning and examinations and will be:

- Immediately documented in the participant's medical record/source document,
- Recorded in the study database
- Reported as outlined below (e.g., Investigational New Drug (IND) Sponsor, IRB, FDA).

If a diagnosis is clinically evident (or subsequently determined), the diagnosis rather than the individual signs and symptoms or lab abnormalities will be recorded as the AE.

All abnormal laboratory findings will be reviewed on a routine basis by the PI or designee to identify potential safety signals. An abnormal lab not included on the toxicity table should be assessed in a similar fashion to the criteria above.

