### Treatment Emergent Adverse Event (TEAE)

A TEAE is any untoward or unfavorable medical occurrence in a human subject, including any abnormal sign (for example, abnormal physical exam, or laboratory finding), symptom, or disease, that manifested after administration of the study treatment, whether or not considered related to the treatment.

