### **12.6 Follow-Up of AEs and SAEs**

AEs that occur following enrollment of the participant after first vaccination will be followed until the final outcome is known or until stable, if chronic, or until the end of the study follow-up period. AEs that have not resolved by the end of the study follow-up period will be recorded as "ongoing." Any participant who experiences complications due to vaccine/placebo administration will be followed until resolution of such complications or appropriate referral to the necessary medical care has been made.

SAEs that have not resolved by the end of the follow-up period will be followed until final outcome is known. If it is not possible to obtain a final outcome for an SAE (e.g., the participant is lost to follow-up),

the reason a final outcome could not be obtained will be recorded by the investigator in the study database and on the SERF.

SAEs that occur after the Day 366 phone call that are reported to and are assessed by the investigator to be possibly, probably, or definitely related will be reported to the CSO, as described above (section 12.4.2 SAEs).

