**Appendix A: Schedule of Procedures/Evaluations**

Study Phase >	Screen	Injec tion 1	Follow -up call	Injec tion 2	Follow -up call	Feedin g	Follow -up	Follow- up	Follow -up	Follow -up call
Study Day >	DAYS -60 to 0	D1	D8	D22	D29	D43	D45	D50	D181	D366
Outpatient Visit	X	X		X		X	X	X		
Comprehension quiz	X									
Written Consent	X									
Medical/Medication History	X	X	X	X	X	X	X	X	X	X
Physician Assessment and PE (targeted and as needed after screening)	X	X		X		X	X	X		
Review of inclusion/exclusion criteria and review of consent	X	X		X						
Vital signs (temperature, heart rate, blood pressure)	X	X		X		X		X		
Vital signs, Vaccine injection site and AE assessment pre-vaccination and 30-45 min post-vaccination		X		X						
Provision of memory aid, ruler and thermometer		X		X						
Review of AEs			X	X	X	X	X	X		
Review of Memory Aid			X		X					
Telephone Call to Assess Symptoms and AEs			X		X				X	X
Pregnancy test (serum/urine) ‡	X	X		X		X				
Vaccine administration		X		X						
Randomization		X								
Mosquito Feeding						X				
Mosquito Bite Assessment						X	X	X		
Safety Labs: hemoglobin, white blood cells, platelets, serum creatinine, serum alanine aminotransferase, random glucose	X	X		X		X		X		
Screening Labs: HIV, hepatitis B and C	X									
Serum and Whole Blood Collection		X				X		X		
Skin Biopsy							X			
Skin Biopsy inspection								X		

† Vital Signs: participants must be sitting for a minimum of 5 minutes before these procedures being performed; vital signs include blood pressure, heart rate, temperature. Weight and height will be taken at the screening visit only.

‡ Serum pregnancy testing at the screening and urine pregnancy testing for all other visits. On Days 1, 22, 43, study vaccination or mosquito feeding will not be initiated until negative results are available. Females of childbearing potential only.

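### Does the missing time window on the primary adverse-event endpoint leave the safety result undefined?

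*Combined protocol and SAP*

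**What the plan says.** Section 3.2 and the Protocol Summary list three primary endpoints. The safety endpoint is "Incidence and severity of treatment emergent adverse events (AEs) and serious adverse events (SAEs" and names no period. The antibody endpoint is limited to "titers from day 1 to day 43", and the cytokine endpoint uses the same interval. The definition of a treatment-emergent event in Section 12.2 covers anything "that manifested after administration of the study treatment, whether or not considered related to the treatment", which gives a start but no end. Section 14.3 says only that adverse events are tabulated by arm.

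Several places suggest Day 50. The Protocol Summary has the study unblinded "once the data from procedures up to day 50 related to the primary and secondary endpoints have been collected for all participants", and Section 3.1 has it "unblinded once all the data for the primary and secondary endpoints and safety data up to day 50 have been collected". Section 14.3.1 plans a safety and immunogenicity report on data to Day 50. The adverse-event review row in Appendix A has its last mark at D50.

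Others suggest Day 366. Section 12.1 says "At each contact with the participant, information regarding AEs will be elicited by appropriate questioning and examinations". Section 12.6 says that adverse events "will be followed until the final outcome is known or until stable, if chronic, or until the end of the study follow-up period", and its special rule for late serious events starts only after the Day 366 call. Appendix A has a row headed "Telephone Call to Assess Symptoms and AEs" that is marked at D181 and D366 as well as at D8 and D29. Section 14.3.1 also labels the Day 50 analysis as interim.

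**The concern.** Incidence means little without its period. Section 14.2 puts safety first among the aims, yet the safety endpoint is the only primary endpoint without a window. Two analysts working from the same database could report different primary incidences, one counting to the Day 50 visit and the other to Day 366.

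Two further worries follow. The Protocol Summary places the Day 181 and Day 366 calls after unblinding, so a 12-month total could mix blinded and open-label reporting. The true rates in Section 14.2 and Tables 1 and 2 also carry no period. If they were 12-month rates and events were counted only to Day 50, the stated chances of seeing a signal would be too high.

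**Working it through.** **What the window changes in the analysis.** Section 14.1 has two hypotheses, both immunological. Section 14.3 gives tabulation as the only analysis of adverse events. A different window would change counts in a descriptive table, but no test or decision threshold.

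**What is collected under either reading.** Adverse events are assessed on Days 1, 8, 22, 29, 43, 45 and 50 (seven contacts) and on Days 181 and 366 (two), so 7 + 2 = 9. All scheduled safety laboratory tests, and the seven-day reactogenicity diaries after each injection (Section 7.2), fall by the Day 50 visit. That visit can move: feeding may be up to 7 days late and the follow-up up to 2, so the latest is Day 43 + 7 + 7 + 2 = Day 59. Section 6.9 mentions only unresolved events at the late calls, but it refers to Appendix A for the procedures. Appendix A and Section 12.1 both have adverse events assessed there.

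**The plan's detection figures.** With *n* participants and true rate *p* (Section 14.2, Tables 1 and 2):

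- Table 1, P(at least 1) = 1 − (1 − *p*)^*n*. For *n* = 10, *p* = 0.15: 1 − 0.85^10 = 0.803 (stated 0.80). For *n* = 40, *p* = 0.07: 1 − 0.93^40 = 0.945 (stated 0.95).
- Table 2, P(at least 2) = 1 − (1 − *p*)^*n* − *np*(1 − *p*)^(*n*−1). For *n* = 10, *p* = 0.27: 0.798 (stated .80). For *n* = 40, *p* = 0.08: 0.841 (stated .84).

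These depend only on *n* and the cumulative rate over whatever period is being watched.

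**The pessimistic scenario.** Suppose the rates were 12-month rates, counting stopped at Day 50, and the hazard were constant. The share of exposure by Day 50 is 49/365 = 0.134. Then:

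- *n* = 10, *p* = 0.15: 1 − 0.85^(10 × 0.134) = 0.20
- *n* = 40, *p* = 0.07: 1 − 0.93^(40 × 0.134) = 0.32

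The plan does not create this scenario. Section 14.2 and both table headings tie the probabilities to halting rules 1 and 2. Section 12.9 sets no end date for counting halting events, and Sections 12.4.2 and 12.13.3 have serious events reported as they arise. A constant hazard is also a poor model here. The halting rules count events judged at least possibly related, and each such category in Section 12.3.2 requires plausible timing relative to the study agent. The last scheduled injection is on Day 22. Related events should cluster early, and if all fall by Day 50 the stated figures stand unchanged.

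**Blinded and open-label periods.** Take the stated two-month accrual as 60 days. The last participant's Day 50 visit then falls when the first enrolled is at Day 60 + 50 = 110 to 60 + 59 = 119. The Day 181 call window opens at Day 181 − 14 = 167. For an early participant to reach that call still blinded, data collection would need a lag of at least 167 − 119 = 48 days, or a longer accrual. That would depart from the sequence in the Protocol Summary. Because the Day 50 report uses data only to that visit, it already isolates the period before planned unblinding.

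**The case for a change.** The best case for a change is that a primary endpoint should not rest on inference, least of all the one serving the objective that the sponsor names first. The wording would cost a sentence. A single 12-month total could blur blinded and unblinded ascertainment in a trial that relies on blinding to limit bias in data collection.

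The textual point stands: the endpoint, the definition and the analysis section are all silent. The documents also do not settle the choice. The unblinding text leans to Day 50, while the open-ended definition and the interim label lean to Day 366, and for serious events a 12-month reading is natural. The contrast with the other primary endpoints is weaker than it looks, because a fold increase cannot be defined without two time points, whereas incidence can default to the whole follow-up.

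What does not stand is the consequence. Neither reading suppresses data or prevents the other figure from being shown, and neither feeds an inferential claim.

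**Conclusion.** No change is needed. The missing window is an omission of detail that the analysts can fill by stating the period on each table: onset up to the Day 50 visit for the planned report, and the full follow-up for the final one. No stated probability, sample size or safety conclusion changes. The uncertainty is confined to events that begin after the Day 50 visit, which come from two of nine contacts and appear in the 12-month tabulation either way.

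This rests on two assumptions. Onset dates must be recorded, which the treatment-emergent definition requires in practice. Events volunteered at the late calls must be recorded as Section 12.1 and Appendix A provide. The low detection figures of 0.20 and 0.32 should not be held against the plan, since they need both a Day 50 cut-off on halting events and a constant hazard, and the documents support neither.

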### Secondary:

1. Geometric mean titer and fold increase in AGS-v PLUS specific IgG, IgM and IgE titers seven days after mosquito feeding (day 50) compared to day 1 and 43.
2. Geometric mean concentration and fold increase in AGS-v PLUS specific Th1 and Th2 cytokine responses in the supernatants of PBMCs (day 50 compared to days 1 and 43) after *in vitro* exposure with AGS-v plus.
3. Survival and fecundity in *Aedes aegypti* and *Aedes albopictus* female mosquitoes after feeding on vaccinated participants.

### Exploratory:

1. Reactions to mosquito bites by size of wheals/papules, redness of the flare, swelling and itching 30 min post-mosquito feeding (day 43), after two days (day 45) and after 7 days (day 50).
2. Early innate immune response to the mosquito bites in AGS-v PLUS vaccinated participants compared to placebo from biopsies taken from the bite site 2 days post-feeding.
3. *In vitro* viability of Zika virus coated in mosquito saliva after incubation with serum and/or PBMCs from vaccinated participants.
4. Geometric mean concentration and fold increase in Th1 and Th2 cytokine responses (from day 1 to day 43, and from day 43 to day 50) after *in vitro* exposure of PBMCs with mosquito saliva from *Aedes aegypti*, *Aedes albopictus* and *Anopheles gambiae*.

## 4 Study Enrollment

Information regarding study materials will be communicated to potential participants who have previously participated in vaccine trials or expressed willingness to participate at the enrollment sites and have signed an authorization form that they are willing to be contacted for future studies. This has been done with institutional review board (IRB) approval. Educational meetings will be offered to the public both within and outside the university system for the purposes of informing individuals of the study. Every effort

will be made to achieve a balanced participant population while avoiding the enrollment of vulnerable populations. Careful screening will be conducted to avoid enrollment of individuals with substance abuse or psychiatric difficulties. Efforts to retain study participants include, but are not limited to: development of professional rapport with potential participants, obtaining valid contact and backup contact information from potential participants, and telephone reminder calls and/or email reminders for upcoming study visits.

The Center for Vaccine Development and Global Health (CVD) will be the site for participant enrollment and inoculation. Mosquito feedings will occur in the Malaria Challenge Suite, where studies of controlled human malaria infection take place. Outpatient follow-up will be conducted at the CVD outpatient clinic.

#### 4.1 Inclusion Criteria

1. Healthy women and men who are  $\geq 18$  and  $\leq 50$  years of age.
2. Willingness to complete all study visits and comply with all study requirements.
3. A male participant is eligible for the study if he agrees to practicing abstinence or using a condom with spermicide plus an acceptable form of contraception (see inclusion criteria 4) being used by any female partner from 4 weeks before study start to 12 weeks after the second vaccine administration.
4. A female participant is eligible for this study if she is not pregnant or breast feeding and 1 of the following:
  - Of non-child bearing potential (i.e., women who have had a hysterectomy or tubal ligation, or are postmenopausal, as defined by no menses in  $\geq 1$  year).
  - Of childbearing potential but agrees to practice effective contraception or abstinence for 4 weeks before study initiation and 12 weeks after the second vaccine administration. Acceptable methods of contraception include a female partner who is the sole sexual partner of the female participant, a male partner who is sterile and is the sole sexual partner of the female participant, or a male partner who uses a condom with spermicide plus 1 or more of the following: 1) implants of levonorgestrel; 2) injectable progestogen; 3) an intrauterine device with a documented failure rate of  $< 1\%$ ; 4) oral contraceptives; and 5) double barrier method including diaphragm.
5. Willing to have samples stored for future research.
6. Agrees to abstain from alcohol intake for 24 hours before each study visit.
7. Agrees to not donate blood or blood products throughout the study.
8. Score  $\geq 70\%$  on comprehension quiz at screening

